4.1.2. Secondary Endpoints

Secondary Efficacy Endpoints:

- Proportion of participants with Investigator's Global Assessment (IGA) = 0 to 1 at each visit from baseline through week 24
- Percent change from baseline in EASI at each visit through week 24
- Absolute change from baseline in EASI at each visit through week 24
- Proportion of participants with EASI-50 ($\geq 50\%$ reduction from baseline in EASI) at each visit through week 24
- Proportion of participants with EASI-75 ($\geq 75\%$ reduction from baseline in EASI) at each visit through week 24
- Proportion of participants with EASI-90 ($\geq 90\%$ reduction from baseline in EASI) at each visit through week 24
- Percent change from baseline in total SCORing AD (SCORAD) and SCORAD component scores at each visit through week 24
- Proportion of participants with SCORAD-50 ($\geq 50\%$ reduction in SCORAD from baseline) at each visit through week 24
- Proportion of participants with improvement (reduction) of weekly average of daily Peak Pruritus (PP) NRS ≥ 3 from baseline at each visit through week 24
- Proportion of participants with improvement (reduction) of weekly average of daily PP NRS ≥ 4 from baseline at each visit through week 24
- Percent change from baseline in weekly average of daily PP NRS at each visit through week 24
- Absolute change from baseline in weekly average of daily PP NRS at each visit through week 24
- Change from baseline in percent BSA at each visit through week 24
- Change from baseline in health-related QOL as measured by Dermatology Life Quality Index (DLQI; age ≥ 16), Children's Dermatology Life Quality Index (CDLQI; age < 16) at each visit through week 24
- Change from baseline in Patient Oriented Eczema Measure (POEM) at each visit through week 24

- Change from baseline in Hospital Anxiety and Depression Scale (HADS) at each visit through week 24
- Change from baseline in Skin Pain NRS (SP NRS) at each visit through week 24
- Change from baseline in weekly average Sleep Quality NRS at each visit through week 24
- Proportion of participants with PGID response as No symptoms at each visit through week 24
- Proportion of participants with PGID response as No symptoms or Mild symptoms at each visit through week 24
- Proportion of participants who rate their eczema symptoms in PGIC as “Much better” at each visit through week 24
- Proportion of participants who rate their eczema symptoms in PGIC as “Much better” or “Moderately better” at each visit through week 24

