11. STATISTICAL PLAN

11.1. Statistical Hypothesis

There is no formal statistical hypothesis testing and no planned inferential comparisons in this study.

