11.2. Justification of Sample Size

The enrolled population will attempt to approximate the US census bureau data on proportions of self-reported races that comprise the skin of color population in the United States— to this end all self-reported races representing skin of color will be included, however a cap at approximately 40% will be set for non-black/non-African American participants.

Due to the descriptive character of this study, no formal sample size calculation will be performed. The sample size of this study is chosen empirically to support descriptive analysis of efficacy and safety in the overall skin of color population. With up to a potential 15% drop out rate based on prior studies, 120 participants would yield approximately 105 participants overall.

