5.7. Analyses of Efficacy Data

The efficacy variables will be summarized for all patients in FAS. The continuous efficacy variables will be summarized using number of patients, mean, SD, median, Q1, Q3, minimum and maximum. Categorical efficacy variables will be summarized using patient counts and percentage. No formal statistical hypothesis testing will be performed. The graph of mean value for continuous variable or proportion for categorical variable by visit will be provided.

Unless otherwise specified, all observed values, regardless of whether data is collected after withdrawal from study treatment will be used for analysis.

Unless otherwise specified, for the categorical efficacy variables, the proportion of patients with each response at each visit will be calculated using the number of patients with a non-missing value at the visit as the denominator.

Subgroup analyses for efficacy

Different subgroups within the FAS population will be defined as below. The analyses will be performed for the primary efficacy variables by:

- Duration of AD (<5 years, \geq 5 years)
- Baseline weight with grouping (\geq 60kg, <60kg for adolescents, <60 kg, \geq 60-<90 kg, \geq 90 kg for adults)
- BMI with grouping (<35, \geq 35-<40, \geq 40)
- Age (\geq 12-<18, \geq 18-<40, \geq 40-<65, \geq 65)
- Sex (Male, Female)
- Race (Black or African American, Asian, Others)
- Fitzpatrick Skin Types phototype (FST 4; FST 5 + 6 [combined])

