For each sub-scale: if one question is missing, the response will be imputed as the mean of the remaining six questions. If more than one question is missing, then the subscale is set to missing. The total score is the sum of the two sub-scores.

HADS will be assessed at time points according to Section [10.2](#).

Skin Pain NRS

Skin pain will be measured using a skin pain NRS that was developed and tested for the study-relevant age group. This is an 11-point scale (0 to 10) in which 0 indicates no pain while 10 indicates worst pain possible. SP NRS can be categorized as: no pain (0), mild (1 to 3), moderate (5 to 6), severe (7 to 9), and very severe (10). The threshold for minimally clinically important difference for SP NRS is between 2.2 to 2.9 ([Silverberg, 2021](#)). The SP NRS will be performed at time points according to Section [10.2](#).

Adult patients will be asked the following question:

- “On a scale of 0 to 10, with 0 being ‘no skin pain or soreness’ and 10 being ‘the worst possible skin pain or soreness’, how would you rate your skin pain or soreness overall, which is on average, during the past 7 days?”

Adolescent patients (≥ 12 to < 18 years at baseline) will be asked the following question:

- “Think about all the areas of your skin with eczema. How would you rate your skin pain at its worst in the past 7 days?”

Patients will be asked to complete this assessment at baseline and then approximately every month throughout the study as indicated in Section [10.2](#).

The baseline Skin Pain NRS score is defined as the prorated average of the Skin Pain scores reported continuously for 7 days right before the baseline visit (i.e. study day -7 to day -1). For post-baseline Skin Pain NRS score, the weekly mean of daily Skin Pain score is calculated as the average of the available reported skin pain score within the week. For example, if there are 3 scores available in a week, the prorated average = $(\text{score1} + \text{score2} + \text{score3})/3$.

Sleep Quality NRS

Study patients will be asked to rate their sleep quality on their past night upon awakening, using the Sleep Quality NRS, ranging from 0 (“Worst possible sleep”) to 10 (“Best possible sleep”). Sleep Quality NRS are to be collected daily including 7 days immediately preceding the baseline visit and then daily during the week before each planned visit.

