Patients will be instructed on using the patient diary to record their Sleep Quality NRS at the screening visit. Clinical sites will check and remind the patient to complete the diary according to the time points in Section [10.2](#).

The baseline Sleep Quality NRS score is defined as the prorated average of the sleep quality NRS scores reported continuously for 7 days right before the baseline visit (i.e. study day -7 to day -1). For post-baseline Sleep quality NRS score, the weekly mean of daily sleep quality score is calculated as the average of the available reported daily sleep quality score within the week. For example, if there are 3 scores available in a week, the prorated average = (score1 + score2 + score3)/3.

Patient Global Impression of Disease (PGID)

The PGID is an assessment instrument used by the patient in clinical studies to rate their eczema symptoms during the past 7 days.

Patients will rate their disease based on the 5-level scale as follows:

“Overall, how would you rate your eczema symptoms during the past 7 days?”

- No symptoms
- Mild
- Moderate
- Severe
- Very severe

The PGID score will be assessed at time points according to Section [10.2](#)

Patient Global Impression of Change (PGIC)

PGIC will be measured using a patient administered tool.

Patients will respond to the following question based on the 7-level scale as follows:

“Compared to before you started the study, how would you rate your eczema now?”

- Much better
- Moderately better
- A little better
- No change
- A little worse
- Moderately worse
- Much worse

The PGIC is an instrument used by the patient in clinical studies to compare their eczema symptoms from the beginning of the study to when they completed the assessment.

The PGIC score will be assessed at time points according to Section [10.2](#).

Colorimetry Measurement (Sub-study)

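### SAP 5.7.2 plans percent change on the raw Sleep Quality NRS, where 10 is best; its mean is inflated toward benefit, so the row should be deleted and absolute change kept

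*SAP*

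**What the plan says.** - **Scale.** SAP 10.3 describes the "Sleep Quality NRS, ranging from 0 (“Worst possible sleep”) to 10 (“Best possible sleep"). It states no reversal and does not say which direction of change is improvement.
- **Protocol endpoint.** Protocol 4.1.2 lists "Change from baseline in weekly average Sleep Quality NRS at each visit through week 24", which is an absolute change.
- **SAP analysis.** The table in SAP 5.7.2 has two rows for this scale: mean and change from baseline, and percent change from baseline. The second is a SAP addition.
- **Denominator.** Under SAP 10.3 the baseline is the "prorated average of the sleep quality NRS scores reported continuously for 7 days right before the baseline visit". The post-baseline value is "calculated as the average of the available reported daily sleep quality score within the week". There is no rule for a baseline of 0.
- **Summaries.** SAP 5.7 says: "The continuous efficacy variables will be summarized using number of patients, mean, SD, median, Q1, Q3, minimum and maximum". It adds: "The graph of mean value for continuous variable or proportion for categorical variable by visit will be provided".
- **Eligibility.** Protocol 7.2.1 requires EASI of at least 16, BSA of at least 10% and a weekly mean PP NRS of at least 4 at baseline. It sets no requirement on sleep.
- **Inference.** Protocol 11.1 says: "There is no formal statistical hypothesis testing and no planned inferential comparisons in this study".

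**The concern.** Percent change divides by baseline. On a scale where high is worse, the sickest participants have the largest denominators and improvement stops at -100%. On the Sleep Quality NRS the sickest have the smallest denominators. Worsening stops at -100% and improvement has no matching limit. A few very poor sleepers can therefore carry the mean, and random fluctuation alone moves the mean upward, which on this scale reads as benefit.

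The study has one arm, so no control group shows the same drift. A favourable mean percentage for sleep would stand beside percentages for itch, POEM, EASI and SCORAD that drift the other way, and a reader would naturally compare them.

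**Working it through.** **Plan's own figure.** The documents give no mean, SD or percent change for Sleep Quality, so there is nothing to reproduce. The only number borrowed is a trial size of 105, from "120 participants would yield approximately 105 participants overall". (120 × 0.85 = 102; the difference is immaterial here.)

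**1. Range of the measure.** Percent change = 100 × (Y − X)/X, where X is baseline and Y is follow-up.
- With seven integer scores the smallest non-zero X is 1/7. The largest improvement is 100 × (10 − 1/7)/(1/7) = +6900%. The largest worsening is -100%.
- X = 0 is undefined.
- The same 2-point gain is 200/X percent: +400% from 0.5, +200% from 1, +100% from 2, +50% from 4 and +25% from 8.

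**2. Direction of the artefact.** If X and Y are positive and exchangeable (no systematic change), then E[Y/X] = E[(Y/X + X/Y)/2] ≥ 1, with equality only if every patient has Y = X. Two-patient check: one goes from 2 to 4 and the other from 4 to 2. The mean absolute change is 0; the mean percent change is (100 − 50)/2 = +25%.

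**3. Size with no systematic change.** All distributions below are assumed. Correlated scaled-beta weekly means on 0 to 10, rounded to 1/7, same distribution at both times:

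| Baseline mean / SD | Correlation | Mean % change, raw score | Mean % change, 10 minus score |
|---|---|---|---|
| 4.5 / 2.2 | 0.5 | about +27% | +17% |
| 4.5 / 2.2 | 0.7 | +16% | +10% |
| 5.5 / 2.0 | 0.5 | +12% | +19% |
| 5.5 / 2.0 | 0.7 | +7% | +11% |

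A positive value is apparent improvement in the third column and apparent worsening in the fourth. At mean 6.5, SD 2.0, the raw figure is +5% to +9%. The median and the absolute change are about 0 throughout.

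A second model simulated the diary itself: seven integer scores a week, day-to-day SD 1.5, baseline mean 3 to 7, between-patient SD 1.5 to 2.5, week-to-week SD 0.7 to 1.5, zero baselines dropped. Over 15 scenarios:
- mean percent change +2% to +49%, above zero in 83% to 100% of trials of 105;
- median percent change -2.7% to 0%;
- mean absolute change -0.01 to +0.01 points;
- baseline of 0 in 0% to 7% of patients;
- on 10 minus the score, apparent worsening of +2% to +48%.

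**4. Size with a real effect.** Same diary model, 2-point shift, between-patient SD 2, week-to-week SD 1:

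| Baseline mean | Mean % change | Median % change | Share of mean from lowest-baseline tenth |
|---|---|---|---|
| 4 | +99% | +47% | 50% |
| 5 | +68% | +37% | 48% |
| 6 | +47% | +28% | 41% |

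Under the beta model, a move from 5.5 (SD 2.0) to 7.0 (SD 2.0) at correlation 0.5 gives a mean of +45% and a median of +26%. The percent change of the group mean is (7.0 − 5.5)/5.5 = +27%.

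**The case against.** The strongest reply is that the safeguards are already in the plan. Absolute change is the row above and is the protocol endpoint. The median, quartiles, minimum and maximum are required for every continuous variable, so a skewed mean would be visible in the same table. Nothing is tested, and this is one supplementary row among many secondary summaries. All of that stands. It limits the weight of the point, but it does not make the mean percent change a sound summary.

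Several stronger readings are tempting, and the documents do not support them:
- **That the measure shows improvement when nothing changes.** If every patient's score is identical at both times, percent change is exactly 0. The artefact needs within-patient variation, and it belongs to the mean.
- **That improvement is literally unbounded.** It lacks a 100% ceiling, but a full integer diary caps it at +6900%.
- **That this is the only scale with a percent-change row that runs in this direction.** SAP 5.7.2 also plans percent change for the Dyspigmentation and Xerosis NRS, and neither document gives the anchors of their severity scores. The contrast can be drawn only with scales whose direction is defined, such as PP NRS, POEM, EASI and SCORAD.
- **That the inflated figure will be plotted.** The graph rule in SAP 5.7 is general and does not name percent change in sleep.
- **That scoring 10 minus the value cures it.** Reversal restores the cap but turns the artefact into apparent worsening. At 5.5/2.0 the distortion is larger after reversal (+19% against +12%).

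The SCORAD row labelled as a sleep NRS, which SAP 10.3 defines as sleeplessness with 10 = worst, is a labelling matter only.

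**Conclusion.** The point holds for the mean percent change of the raw Sleep Quality NRS. Its direction follows from algebra once baseline and follow-up are exchangeable. Its size depends on assumed distributions: about +5% to +28% with no systematic change under the beta model, and +2% to +49% over the wider diary scenarios. With a real 2-point shift, the simulated mean is roughly 1.7 to 2.1 times the median (47/28 to 99/47). The absolute change is free of the artefact and the median nearly so.

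This is a minor point. It does not show that the trial's sleep finding will be wrong, because the protocol's sleep endpoint is absolute change. The primary endpoint is unaffected.

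**What to change.** In SAP 5.7.2, delete the percent-change row for Sleep Quality NRS and keep mean and absolute change. In SAP 10.3, state that a positive change is improvement.

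If a percentage is wanted, report either the median and quartiles of percent change only, with a stated rule for a baseline of 0, or the percent change of the group mean. Do not present or plot the mean percent change, and do not rely on reversing the score.

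The cost is one supplementary row that the protocol does not ask for. The change is to SAP wording only, and SAP section 1 already allows revision of the plan during the study.
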